7.6 Other Variables

The analysis will be performed by MP treatment group (high, mid, low) and in total. Tables for the SES will be created according to the actual treatment group and tables for the FAS will be created for the MP treatment group as randomized. Subject dispositions, demographic data, GMFCS-E&R level at Screening, and baseline characteristics will be presented using standard descriptive statistics; no homogeneity tests will be performed. Demographic data, GMFCS-E&R level at Screening and treatment compliance will be summarized for the SES of the MP, the FAS of the MP, the PPS of the MP, the SES of the OLEX, and the FAS of the OLEX. Demographic data and GMFCS-E&R level at Screening will be given for all randomized subjects in addition. The remaining baseline data such as CP history (including main cause for cerebral palsy, affected limbs, duration since first diagnosis of spasticity, and duration since the first diagnosis of cerebral palsy), primary clinical pattern, planned treatment of spasticity, BoNT-A pre-treatment status at screening and use of local anesthesia/analgesia for injection treatments will be summarized descriptively only for the FAS of the MP, the PPS of the MP, and the FAS of the OLEX (AS scores at baseline will be displayed in the efficacy section 14.2.). The information, if monitoring was done during sedation of subjects will be listed. Injection guidance technique will be listed for each treated clinical pattern.

The absolute and relative frequencies for subject's reason for premature study discontinuation will be tabulated. Further, the main reason will be tabulated by using the following approach for identification: chose from the reasons that are documented for a subject that one that occurs first in the list as main reason. The list is as follows:

1. Death
2. Pregnancy
3. Adverse Event(s)
4. Lack of efficacy
5. Withdrawal by subject
6. Physician decision
7. Protocol violation
8. Lost to follow-up
9. Other

The analysis of BoNT-A pre-treatment status includes frequency tables for:

- number pre-treated/naïve subjects
- Botulinum Toxin preparations used since first treatment
- Botulinum Toxin preparation used at most recent injection session
- specification of limbs and body side of the most recent pre-treatment

and descriptive summary statistics for:

- number of pre-treatments

- duration since first treatment with Botulinum Toxin
- duration since most recent injection session prior to study entry
- total body dose of Botulinum Toxin at most recent injection session

With respect to pre-treatment with Botulinum Toxin the following durations will be calculated:

- Duration since first treatment with Botulinum Toxin [months] = (date of first injection (V2) – date of first treatment with Botulinum Toxin) + 1 / 30.5
- Duration since most recent injection session prior to study entry [months] = (date of first injection (V2) – date of most recent injection session prior to study entry) + 1 / 30.5

In case of missing days, the date will be set to the first day of the respective month. In case the month is also missing, no imputation will be done and the duration will be defined as missing.

The duration since the first diagnosis of spasticity and the duration since the first diagnosis of cerebral palsy in months will be calculated as follows:

- Duration since diagnosis [months] = (date of first injection (V2) - date of first diagnosis) + 1 / 30.5

In case of missing days, the date will be set to the first day of the respective month. In case the month is also missing, no imputation will be done and the duration will be defined as missing.

Regarding planned treatment of spasticity frequency tables will be created for treatment combinations A, B, C, D, and E, limbs planned to be treated (lower limb right, lower limb left, upper limb right, and upper limb left), and primary body side chosen for analyses.

Treatment compliance for each injection visit (V2, V6, V10, and V14) will be calculated as follows:

- Total Compliance per injection cycle [%] = $100 * \text{Total volume injected in all 4 limbs [mL]} / \text{Total planned volume for all 4 limbs according to treatment combinations A, B, C, D, and E and body weight.}$
- Compliance per injection cycle and per limb [%] = $100 * \text{Total volume injected in limb [mL]} / \text{Total planned volume for limb according to treatment combinations A, B, C, D, and E and body weight.}$

For the overall OLEX Period the following is calculated in addition:

- Total compliance of the OLEX Period is calculated as mean compliance per subject for all performed injection cycles of this subject in the OLEX Period.

Treatment compliance will be displayed using descriptive summary statistics and frequency table for classified compliance per injection visit, primary body/non-primary body side, upper/lower limb(s) in total for these categories. Separate listings will be given for all subjects with total treatment compliance per cycle >100% for the SES of the MP and for the SES of the OLEX period.

Frequencies of previous and concomitant treatments of the MP will be given based on different Anatomical Therapeutic Chemical classification (ATC) code levels of the World Health Organization (WHO) dictionary version MAR 2018 as well as by generic name for the SES of the MP, the FAS of the MP, and the PPS of the MP. Frequencies of concomitant treatments of the OLEX period will be given based on different ATC code levels as well as by generic name for the SES of the OLEX and the FAS of the OLEX. Indications for previous and concomitant therapies will not be coded and will only be listed. Medical history and concomitant diseases well as non-drug treatment of the MP will be described based on MedDRA SOC and PT levels for the SES of the MP. Concomitant diseases well as non-drug treatment of the OLEX period will be described based on MedDRA SOC and PT levels for the SES of the OLEX.

The analysis of extent of exposure, length of injection cycles and total observation period as described below will be performed for the SES of the MP or the SES of the OLEX period, respectively.

Descriptive statistics will be generated for injected volume and injected units, number of injected sites. The analysis will be done per body side, clinical pattern, primary clinical target pattern, and per muscle including 'total' for each of these categories.

Frequency tables will be given for treated limbs at each injection visit V2, V6, V10 and V14 (lower limb right, lower limb left, upper limb right, and upper limb left). The number and percentage of subjects with unilateral treatment and with bilateral treatment for upper limbs and for lower limbs will be tabulated.

Descriptive statistics will be generated for length of injection cycle, and the total observation period in weeks over the entire study, for MP and for OLEX period. Frequency tables will be given for classified injection cycle length by injection cycle. The following classes will be used:

- < 12 weeks
- 12 – 16 weeks
- > 16 weeks

The injection visit will be regarded as start of a cycle and the day before the next injection (or the last available visit in case of a discontinued cycle or the last cycle) will be regarded as end of cycle. Length of injection cycle and observation period in weeks will be calculated as follows:

- Total observation period in weeks over the entire study will be calculated as date of last available study visit (e.g. V17 for completers) - date of baseline visit V2 +1 day.
- Observational period of the MP in weeks will be calculated as:

Date of first injection in the OLEX V6 - date of baseline visit V2, if V6 is available.

Date of last available visit of the MP (e.g. V5 for completers of the MP) - date of baseline visit V2 +1 day, if V6 is not available.
- Observational period of the OLEX in weeks will be calculated as date of last available visit of the OLEX (e.g. V17 for completers) - date of first injection in the OLEX V6 +1 day.
- The injection cycle length of injection cycle (x) in weeks will be calculated as
 - Date of injection cycle (x+1) - date of injection (x) **or**
 - Date of last available visit – date of injection (x) +1 day in case of last or discontinued cycle

If injection cycle was not performed length of injection cycle will be missing.

7.7 Special Statistical/Analytical Issues

7.7.1 Discontinuations and Missing Data

Discontinued subjects will not be replaced.

The primary and secondary efficacy variables of the Ashworth scale score will be analyzed on the FAS and PPS of the MP using MMRM for accounting for missing data. The model will be based on the observed cases data without imputing missing values. As sensitivity analysis for the primary efficacy variable and for the secondary efficacy variables of the AS score an ANCOVA model without repeated measures will be applied. The LOCF principle will be followed on the FAS and PPS of the MP, i.e., the last observation (including baseline) will be carried forward to Week 4 and all further visits with missing values. In addition, further sensitivity analysis for the primary and secondary efficacy variables, the so called observed case analysis without missing data replacement, will be performed on the FAS and PPS of the MP to explore the impact of the respective missing imputation principle.

In case of missing data in the co-primary variable these will be imputed by “0” (no change). Assuming a similar percentage of missing data in all three treatment arms this imputation

leads to a decreased difference of the treatment effects. For this reason the “no change” imputation is considered as conservative approach.

As the GICS is only measured at Control Visit V3, it is not possible to apply a model based analysis like mixed model repeated measurement. Therefore, only ‘no change replacement’ and observed case analysis as sensitivity analysis will be performed.

For the secondary efficacy variable ‘Questionnaire on Pain caused by Spasticity’ LOCF and observed case analyses will be performed on the FAS and the PPS. For the secondary efficacy variable ‘Global Impression of Change Scales’ missing values will be replaced by “0” (no change) and an observed case analyses will be performed on the FAS and the PPS.

For child’s/adolescent’s GICS and QPS the observed case analysis is the main analysis of interest, and the ‘no change replacement’ (GICS) and the LOCF (QPS) are the respective sensitivity analyses.

Missing assessments except for primary or co-primary efficacy variable will not be listed as protocol deviations.

Observed case analysis will be performed for all efficacy data of the OLEX period, i.e. missing data of the OLEX will not be replaced.

7.7.2 Interim Analyses

No formal interim analyses are planned.

An overall study report will be written after completion of OLEX, giving the efficacy and safety results of the entire study.

7.7.3 Data Monitoring Committee

An independent data monitoring committee (DMC) will be assigned to monitor subject’s safety throughout the clinical course of the study. It will consist of an uneven number of physicians, e.g., three physicians, to achieve a decision of majority. DMC members must be experienced in the indication and population and will not be involved in any study conduct sponsored by Merz. An independent biostatistician may complement the DMC. The primary purpose of the DMC is to safeguard the subject. The DMC provides a mean to rapidly note an unexpected hazard that may lead to study termination.

On a regular basis the DMC will evaluate safety data of this study to ascertain protection of subject's safety. The DMC will be kept informed by a DMC office manager who is not involved in this study and located at a contract research organization. The DMC will convene at regular intervals to discuss and decide upon safety issues.

Safety data will be evaluated without knowledge of efficacy data. The treatment code of an individual subject may be unblinded within the DMC if necessary for the safety evaluation. Detailed procedures for the evaluation of safety data and unblinding will be laid down in the DMC charter. All safety aspects with lifted blind discussed during DMC meetings will be provided for filing in the trial master file only after data base lock and subsequent unblinding of the study.

If indicated, the DMC will advise Merz and make recommendations regarding e.g., subject's withdrawals and/or study measures. Details on responsibilities and procedures to be followed by the DMC will be laid down in the DMC Charter.

7.7.4 Multiple Comparisons/Multiplicity

Testing of the primary, co-primary and key-secondary efficacy variables will be performed in a 4-step approach using a hierarchical test procedure as described in section 7.1.1 and 7.1.2. If one of the four hierarchical tests does not yield a statistically significant result, the consecutive test(s) will still be performed but will be considered to be only descriptive. Whenever two variables are tested in one step (step 1, 2, and 4), both variables have to show statistically significant treatment differences in order to prove superiority over low dose treatment in this step. For this reason no α -adjustment for multiplicity is necessary in these combined tests of two variables. This four step hierarchical testing procedure ensures the overall type I level of 5% for the confirmatory tests.

7.7.5 Examination of Subgroups

Subgroup analyses will be performed for the AS regarding treatment group, pooled sites, BoNT-A pre-treatment status, GMFCS-E&R level groups at Screening, AS baseline value, age (2-5, 6-11, 12-17 years), weight group at baseline (<25 kg, \geq 25 kg), use of local anesthetics and/or analgosedation and unilateral versus bilateral treatment. Shift tables and frequency tables of changes will not be presented for subgroup analyses.

Subgroup analysis for TEAEs, related TEAEs, serious TEAEs and TEAEs of special interest by SOC and PT will be performed for the following subgroups: GMFCS-E&R level groups, age (2-5, 6-11, 12-17 years), weight group at baseline (<25 kg, \geq 25 kg), and use of local anesthesia/analgosedation for injection treatment.

The following TEAESIs will be analyzed by UL treated, LL treated, not applicable (not located at any treated limb):

- Muscular weakness

- Monoparesis
- Hemiparesis
- Paralysis
- Paralysis flaccid
- Paraparesis
- Paresis
- Peripheral nerve palsy
- Peripheral paralysis
- Quadriparesis

For this analysis “UL treated” means that the AE is located at an upper limb, which was treated. “LL treated” means that the AE is located at a lower limb, which was treated. “Not applicable” means that the AE is not located at any treated limb.

For the subgroup analysis ‘use of local anesthetics and/or analgosedation’ the two following subgroups will be analyzed:

- Subjects with use analgesics and/or sedatives been used during corresponding injection
- Subjects without use analgesics and/or sedatives been used during corresponding injection

For the subgroup analysis regarding ‘unilateral versus bilateral treatment’ the following subgroups will be defined for analysis of the AS score of the ULs:

- Unilateral treatment of the upper limbs (Treatment combination A if unilateral, B, C and D)
- Bilateral treatment of the upper limbs (Treatment combination A if bilateral and E)

For analysis of the AS score of the LLs the following subgroups will be analyzed:

- Unilateral treatment of the lower limbs (Treatment combination B)
- Bilateral treatment of the lower limbs (Treatment combination C, D and E)

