### 4.3 Risk-benefit assessment

There is no monitored experience in children/adolescents available for the BoNT-A preparation under investigation. NT 201 was subject to extensive toxicological and safety pharmacological testing in non-clinical as well as clinical studies, which showed that NT 201 is well tolerated and has an acceptable safety profile (see current IB [[Merz Pharmaceuticals \(GmbH\) - IB](#)]). In a juvenile toxicity study in rats, decreased mating rates and atrophy of the testicular germinal epithelium with subsequent hypospermia without functional consequences were observed at 30 Lethal Dose 50 (LD50) Units [LD50U]/kg. However, no indications of frank systemic toxicity other than growth retardation were seen at 10 LD50U/kg and below. The clinical relevance of the findings from this animal study with these extremely high doses and reinjection already at

maximal paralysis is unknown. In a clinical setting, subjects are only re-injected upon recovery of the muscle function, usually 3 to 6 months after injection of BoNT-A. In this study investigators who are informed on preclinical safety data of NT 201 will judge the clinical need for an injection in doses of up to a maximum of 20 U/kg BW NT 201 at least 12 weeks after the last injection treatment. Two clinical studies with NT 201 in adult subjects with UL muscle spasticity after stroke and other etiologies with a maximum dose of 400 U NT 201, respectively, showed good efficacy and no safety issues [Barnes 2010, Kanovsky 2011].

In general, BoNT-A is well tolerated in children/adolescents [Naumann and Jankovic 2004, Lukban 2009, Heinen 2010]. Common undesirable effects after BoNT-A injection include local, generalized, or procedural AEs. Local AEs are usually mild and self-limiting. The most commonly reported local AEs after BoNT treatment in children/adolescents are potential and expectable consequences of overshooting muscle relaxation such as excessive localized weakness [Love 2010]. Systemic AEs related to BoNT-A include nausea, fatigue, bladder incontinence, flu-like symptoms, and rash [Naumann 2006, Howell 2007]. Procedural AEs include complications due to local anesthesia or analgosedation before injection.

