3 CLINICAL STUDY DESIGN AND OBJECTIVES

3.1 Clinical Study Design

This is a prospective, multicenter, multi-national, randomized, double-blind, parallel-group, dose-response study in phase 3 of three doses NT 201. Subjects with upper limb spasticity alone or with combined upper limb (UL) and lower limb (LL) spasticity due to cerebral palsy (CP) will be treated. The study comprises a Main Period (MP) with a single double-blind treatment cycle with three dose arms (high, mid, low), followed by three open-label extension (OLEX) treatment cycles with a single treatment arm using the high dose regimen of MP. Each of the four treatment cycles has an observation period of 12 to 16 weeks, i.e. 14 weeks \pm 14 days.

Treatment of UL(s) in MP will be administered in three parallel dose groups of NT 201 with fixed doses to UL(s):

- In the high dose group 8 U/Kg BW NT 201 (maximum dose per UL: 200 Units (U) for subjects \geq 25kg BW).
- In the mid dose group 6 U/kg BW (maximum of 150 U) per UL.
- In the low dose group 2 U/kg BW (maximum of 50 U) per UL.

As clinically needed, UL treatment can be administered unilaterally or bilaterally and subjects may receive additional Botulinum Toxin (BoNT) injections in one out of five predefined treatment combinations (A-E) up to the maximum total dose applicable for their Gross Motor Function Classification System expanded and revised version (GMFCS-E&R) level (I-III: 20 U/kg BW NT 201, maximum of 500 U; IV and V: 16 U/kg BW NT 201, maximum of 400 U):

- Treatment Combination A: Unilateral or bilateral UL treatment only
- Treatment Combination B: Unilateral UL and unilateral LL treatment
- Treatment Combination C: Unilateral UL and bilateral LL treatment in GMFCS-E&R level I-III
- Treatment Combination D: Unilateral UL and bilateral LL treatment in GMFCS-E&R level IV-V
- Treatment Combination E: Bilateral UL and bilateral LL treatment in GMFCS-E&R level I-III

In MP only, LL(s) treatment will be performed within the same dose groups as UL treatment, i.e. subjects in the mid and low dose group will receive 75% or 25%, respectively, of the dose in the high dose group to all limbs treated.

A total of 344 subjects (2 : 1 : 1 ratio) will be enrolled with:

- At least 172 subjects randomized to the high dose group.
- At least 86 subjects to the mid dose group.
- At least 86 subjects to the low dose group.

The study includes the following visits:

Screening:

Screening Visit (V1): Day -14 (Week -2) ± 5 days

Main Period (MP):

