For any missing data of adverse events, a worst case strategy will be applied for all analysis tables. The intensity will be imputed by the worst intensity “severe”, the causal relationship will be imputed by the worst relationship “drug related”. Missing data of the worst outcome will be imputed by “unknown”. If a subject has more than one outcome within a preferred term (PT) only the worst outcome will be used in the frequency tables. Also on subject level only the worst outcome category per subject will be counted in the frequency table. The worst outcome is defined in the following order:

- recovered/resolved
- recovered/resolved with sequelae
- recovering/resolving
- not recovered/not resolved
- unknown
- fatal

TEAESIs are defined as TEAEs that are thought to possibly indicate toxin spread. A list of adverse events of special interest possibly indicating toxin spread is given in **Table 1: List of Adverse Events of Special Interest Possibly Indicating Toxin Spread.**

Table 1: List of Adverse Events of Special Interest Possibly Indicating Toxin Spread

MedDRA PT	MedDRA PT
Accommodation disorder	IIIrd nerve paresis
Areflexia	Ileus paralytic
Aspiration	IVth nerve paresis
Botulism	Monoparesis
Bradycardia	Muscular weakness
Bulbar palsy	Paralysis
Constipation	Paraparesis
Cranial nerve palsies multiple	Paresis
Cranial nerve paralysis	Paresis cranial nerve
Diaphragmatic paralysis	Peripheral nerve palsy
Diplopia	Peripheral paralysis
Dry mouth	Pelvic floor muscle weakness
Dysarthria	Pneumonia aspiration
Dysphagia	Pupillary reflex impaired
Dysphonia	Quadriparesis
Dyspnoea	Respiratory arrest
Extraocular muscle paresis	Respiratory depression
Eyelid function disorder	Respiratory failure
Eyelid ptosis	Speech disorder
Facial paralysis	Trigeminal nerve paresis
Facial paresis	Urinary retention
Hemiparesis	Vision blurred
Hypoglossal nerve paresis	Vocal cord paralysis
Hyporeflexia	Vocal cord paresis
Hypotonia	
Wording of PTs is according to MedDRA version 21.0	

To fulfill FDA requirements, TEAE data will be screened for suicidal events. The MedDRA PTs of all TEAEs will be checked using standard MedDRA query (SMQ) „Suicide/self-injury“. Resulting TEAE findings will be listed in a separate listing. A list of the MedDRA PTs of the SMQ „Suicide/self-injury is given in Table 2.

Table 2: List of Adverse Events of Standard MedDRA Query „Suicide/self-injury“

MedDRA PT:	MedDRA PT:
Columbia suicide severity rating scale abnormal	Self injurious behaviour

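### The SAP's location breakdown of ten weakness and paresis TEAESIs has no class for an event that involves a treated limb and also an untreated limb or region

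*SAP*

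**What the plan says.** SAP 7.5.2 gives the purpose of the event group: "TEAESIs are defined as TEAEs that are thought to possibly indicate toxin spread". SAP 7.7.5 then takes ten terms, among them muscular weakness, hemiparesis, paraparesis and "Quadriparesis", and specifies: "The following TEAESIs will be analyzed by UL treated, LL treated, not applicable (not located at any treated limb").

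The classes are defined as follows:
- *UL treated*, by its definition, "means that the AE is located at an upper limb, which was treated".
- *LL treated* is worded in the same way for a treated lower limb.
- *Not applicable*, by contrast, "means that the AE is not located at any treated limb".

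Neither treated-limb definition says that the event must be confined to the treated limb. The section has no rule for an event at several sites. It also does not say whether one event may count under both UL and LL.

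Untreated limbs are part of the design. SAP 3.1 lists "Treatment Combination A: Unilateral or bilateral UL treatment only", and among the five combinations only E treats all four limbs. Under SAP 7.5, safety analyses are shown in total and by MP treatment group.

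**The concern.** Weakness near the injection site and weakness further away carry different information in this trial. Protocol 4.3 describes the commonest local events as "potential and expectable consequences of overshooting muscle relaxation such as excessive localized weakness". Protocol 8.2.6, by contrast, lists symmetric descending paralysis and generalised weakness among the signs of excessive dose. In the SAP text available, this breakdown is the only one that sorts adverse events by body site, so it is where a reader would look for the distinction.

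Symmetric or generalised weakness will usually include an injected limb. The stated rule then places it in the same column as weakness confined to that limb, and only weakness that spares every injected limb stands apart. A reader comparing dose groups in this table could not see how many events went beyond the injected limbs.

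**Working it through.** No power, alpha or sample-size figure is involved, so there is no planned number to reproduce. The check applies the three definitions literally.

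**Inputs**
- Class definitions: SAP 7.7.5.
- Treated limbs per combination (SAP 3.1): A unilateral 1, A bilateral 2, B 2, C and D 3, E 4. Protocol 8.1.1.2 adds that the lower limb in B is on the same side as the upper limb.
- Meaning of the terms (assumed, since the documents do not define them): quadriparesis is all four limbs, hemiparesis the arm and leg of one side, paraparesis both legs.

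**Rule**
- Untreated limbs involved = limbs involved − treated limbs involved.
- At least one treated upper (lower) limb involved gives *UL treated* (*LL treated*).
- *Not applicable* only if treated limbs involved = 0.

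| Event | Combination | Limbs involved | Treated | Untreated | Class under the SAP |
|---|---|---|---|---|---|
| Quadriparesis | A unilateral | 4 | 1 | 4 − 1 = 3 | UL treated |
| Quadriparesis | A bilateral | 4 | 2 | 4 − 2 = 2 | UL treated |
| Quadriparesis | B | 4 | 2 | 4 − 2 = 2 | UL and LL treated |
| Quadriparesis | C, D | 4 | 3 | 4 − 3 = 1 | UL and LL treated |
| Quadriparesis | E | 4 | 4 | 4 − 4 = 0 | UL and LL treated |
| Hemiparesis, treated side | A | 2 | 1 | 2 − 1 = 1 | UL treated |
| Paraparesis | B | 2 | 1 | 2 − 1 = 1 | LL treated |

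Weakness of a treated upper limb that also involves a non-limb region, such as the trunk, is *UL treated* in every combination, including E.

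**Wider check.** Eight illustrative event locations were crossed with five treated-limb layouts (A unilateral, A bilateral, B, C/D, E), giving 8 × 5 = 40 cells:
- 14 cells involve a treated limb and also an untreated limb or non-limb region. All 14 fall in a treated-limb class and none in *Not applicable*.
- 12 cells involve no treated limb and are *Not applicable*.
- The remaining 40 − 14 − 12 = 14 cells lie wholly within treated limbs.

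The 14 mixed and the 14 confined cells thus share the same columns. The counts show how the rule works. They depend on the locations chosen and are not expected frequencies.

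**The case against.** The case against giving this much weight is sound in several respects.

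- **Nothing is lost elsewhere.** SAP 7.5.2 provides TEAE incidences by system organ class and preferred term, with listings and, where applicable, tables for events of special interest. SAP 7.5 gives these by MP group. Protocol 10.3 has the DMC review all events of special interest. A reader might infer that the trial's dose-group comparison of possible toxin spread is understated. The documents do not support that, because TEAESI counts by dose group are the same under any location rule.
- **The SAP never calls the treated-limb columns local.** An event at a treated arm counted under *UL treated* is classified as defined. It would go too far to say that the plan declares such events local or files them wrongly.
- **Some terms speak for themselves.** Quadriparesis stays visible as quadriparesis in any output by preferred term. The harder cases are unspecific terms such as muscular weakness or paresis, where the term does not show the extent.
- **Detection of spread does not rest on this table.** SAP Table 1 has about 40 further terms outside it, including botulism, dysphagia and respiratory failure.
- **Overlap and label are not errors.** The SAP does not claim that the UL and LL classes are exclusive, and *Not applicable*, though an awkward label, is defined in the same section.

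One could also read 'located at' as 'wholly located at'. If only the treated-limb definitions are read that way, a mixed event has no class. If the third definition is read that way too, mixed events join the remote ones, together with events spanning two treated limbs. The SAP states neither reading, so a rule is missing in any case.

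What remains is that the outputs by preferred term carry no location split, and DMC review does not change a table in the study report.

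**Conclusion.** The gap is real and follows from the definitions themselves. On their plain reading, an event that involves a treated limb and also an untreated limb or region enters *UL treated* and/or *LL treated* and cannot enter *Not applicable*. In this table such weakness is indistinguishable from weakness confined to the injected limbs, so distant involvement can be under-counted but not over-counted.

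The scope is one descriptive breakdown of ten terms. No confirmatory test, sample size, overall TEAESI count, listing or DMC review is affected. The documents give no rates for these terms, so the number of events concerned is unknown and may be small.

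The conclusion assumes the ordinary meaning of the multi-limb terms and the plain reading of 'located at'. How the location of an event is recorded is not shown: the adverse event items listed in Protocol 10.1 do not include it, and the special-interest report form is not reproduced. If sites enter one record per location, some events would be split, but a single record of quadriparesis or hemiparesis would still span limbs. The change is worth making because the table otherwise cannot show the distinction for which a reader would consult it.

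**What to change.** Replace the three classes in SAP 7.7.5 with exclusive ones:
1. Confined to treated limb(s), shown as UL, LL or both.
2. Involving any untreated limb or body region, alone or together with a treated limb.
3. Location not reported.

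Tabulate them by MP treatment group and by OLEX cycle. Assign the class from the recorded location, the preferred term and the special-interest event report. Cases that these do not resolve go to medical review, which for MP events must be finished before the MP is unblinded.

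The cost is a paragraph of SAP text, one re-specified table and a small review effort. Whether the recorded data are enough to assign every event cannot be confirmed from the documents. If only one location was recorded, some events may have to stay in class 3, and the table should show that number.
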